Randomized Clinical Trial of Exparel vs Pain Pump for Post-operative Pain Control after Total Shoulder Arthroplasty

INTRODUCTION

Routine anesthetic care for patients undergoing a Total Shoulder Arthroplasty (TSA) at our institution includes the implantation of a pain pump. A pain pump is used to allow pain control in the days after a TSA. Anecdotally patients complain of breakthrough pain the night after their surgery when the local anesthetic administered during surgery starts wearing off [Abdallah].

Exparel (Bupivacaine liposome injectable suspension), a sustained-release preparation of bupivacaine that is FDA approved for administration at the surgical site, may provide a lower-cost alternative to a pain pump, as it has the potential for activity up to 72 hours after surgery [Davidovitch, Golf, Haas]. Two prior randomized clinical controlled trials have compared Exparel to an intraoperative interscalene block and showed improved pain scores and less opioid consumption at 24 hours after surgery. There have been no studies comparing Exparel to a pain pump and evaluated the outcomes beyond 24 hours after surgery.

The primary objective of this study is to determine if Exparel leads to better pain scores at 24, 48 and 72 hours after TSA compared to a pain pump. Secondary objectives are (1) to determine if patients on Exparel use less narcotics and (2) have earlier return of functional use of the involved arm after surgery compared to the pain pump.

METHODS

Sample size:

Based on prior studies on anesthetics for TSA, the mean worst pain score in the 24 hours after surgery was 5.4, based on a 0 to 10 scale. To detect a change of 2 points, alpha of 0.05, beta of 0.80, a sample size of 51 subjects in each group will be required. To account for drop-outs, a total of 60 subjects in each arm will be enrolled.

Inclusion criteria

- Patients undergoing unilateral primary TSA or reverse TSA
- Indication for surgery is osteoarthritis, rotator cuff arthropathy or massive irreparable rotator cuff tears
- Surgery performed by the Principal Investigator ([name])
- Anesthesia administered by Co-Principal Investigator ([name])
- Willing and able to sign an Informed Consent

Exclusion criteria

- Indication for surgery is fracture
- Comorbid psychiatric diagnosis requiring therapy and/or medication except anxiety or depression
- Comorbid chronic pain syndrome (reflex sympathetic dystrophy, fibromyalgia)
- Has hepatic disease
- On workers compensation/disability/litigation
- Known adverse reaction to medications to be administered

- On long-acting narcotic pain medication (including extended release narcotic pain medications and methadone)
- Home Oxygen requirement whether PRN or scheduled.
- Contralateral Phrenic Nerve paralysis / incompetence.
- BMI ≥ 50
-

Randomization will be a varied blocked randomization with blocks of 12, 15 and 18 using sealed envelopes

Treatment arms:

Control: Pain catheter based pain control. Subject will receive an interscalene block with Ropivacaine 0.5% (20cc), and then a pain pump attached in the PACU infusing at 4cc/hr. The patient will go home with that device until it runs out.

Interventional: Single shot Exparel 10cc (133mg) mixed with 10cc of 0.5% Bupivacaine

Both arms will receive the same multimodal analgesia medications preoperatively. Celebrex 400mg PO, Gabapentin 600mg PO, Tylenol 1 gram PO, unless contraindicated.

Variables collected

Pre-operative

Age

Sex

Race/Ethnicity

Educational Level

Height

Weight

Side of Arthroplasty

Current pain medication

Pain (NRS, 10 to 10)

ASES

SANE

Work status

Annual income

Days off work

In Hospital

ASA score

Local anesthesia start time

Local anesthesia end time

Operative time

Length of hospital stay

Cumulative MMEs consumed at 24, 48 and 72 hours

Worst pain in past 24 hours at 24, 48 and 72 hours post-op

Duration of sleep

Intraoperative complications

Postoperative complications

Pump failure (Yes/No) queried at 24, 48 and 72 hours

Catheter migration (Yes/No) queried at 24, 48 and 72 hours

Functionality of surgical arm at 24, 48 and 72 hours

Unable to use, Only light activity, Able to do some activities, Able to do most activities, Slight restrictions only, Normal

Six weeks post-operative

Current pain

ASES

SANE

Complications

Three months post-operative

Readmissions

Visits to the Emergency Room

Total costs for Index surgery and all readmissions and Emergency Room Visits

Date returned to work

Statistics:

Baseline data will be compared

ANCOVA or GEE to examine differences in worst pain scores over 24 hours over time between the two groups (among the three groups)

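### The sample-size statement gives beta as 0.80, which means 20% power; no SD possible on a 0 to 10 scale makes 51 per group match that.

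*Combined protocol and SAP*

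**What the plan says.** The justification is one short paragraph, METHODS, Sample size. From prior studies it takes that "the mean worst pain score in the 24 hours after surgery was 5.4, based on a 0 to 10 scale". It then sets the design: "To detect a change of 2 points, alpha of 0.05, beta of 0.80, a sample size of 51 subjects in each group". Enrolment is raised for attrition: "To account for drop-outs, a total of 60 subjects in each arm will be enrolled".

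The paragraph does not give the SD, whether alpha is one- or two-sided, the test, the drop-out rate or a separate figure for power. Nothing elsewhere in the document supplies them or corrects the beta. The primary objective in the INTRODUCTION is "better pain scores at 24, 48 and 72 hours after TSA", so three time points. The Statistics section leaves the choice between ANCOVA and GEE open and refers to both two and three groups.

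**The concern.** Beta is the probability of missing a true difference, and power is 1 − beta. A beta of 0.80 is therefore a plan to detect a 2-point difference one time in five. Few readers will believe that was intended, but it is the only statement of power in the document.

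Two things are at stake. First, the stated power is wrong as written if the figure is a mislabel. Second, a reader who substitutes 80% cannot verify it, because the SD that would turn a 2-point difference into 51 per group is missing. The document then holds no statement of power that is both correct and checkable.

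**Working it through.** **Inputs from the Sample size paragraph:** difference 2 points; alpha 0.05; beta 0.80 as written; 51 evaluable per group; 60 enrolled per arm; mean worst pain 5.4 on a 0 to 10 scale.

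**Assumptions, because the plan is silent:** a two-sample comparison of means with equal groups. Two-sided 0.05 is the main case. One-sided 0.05, and two-sided 0.05/3 for three time points, are variants; the plan mentions no multiplicity adjustment.

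**Step 1. Can 51 be reproduced?** Not directly, since there is no SD. The question becomes which SD 51 per group implies. In the normal approximation

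n = 2 × SD² × (z_alpha + z_power)² / difference², so SD = difference × √(n/2) / (z_alpha + z_power).

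Here 2 × √(51/2) = 10.10.

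**Step 2. Literal reading, power 0.20.** z_power = −0.842, and two-sided z_alpha = 1.960.

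SD = 10.10 / (1.960 − 0.842) = 9.03. The noncentral t calculation gives 8.97.

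**Step 3. Largest SD the scale allows.** For a score bounded by 0 and 10 with mean m, the SD cannot exceed √(m × (10 − m)). At m = 5.4 this is √(5.4 × 4.6) = 4.98. Over all means the maximum is 5.0, at m = 5.

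**Step 4. Compare, using the t test with 51 per group and a difference of 2.**

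| Reading of alpha | SD needed for 20% power | Power at SD 4.98 | SD implied by 80% power |
|---|---|---|---|
| Two-sided 0.05 | 8.97 | 52% | 3.57 |
| One-sided 0.05 | 12.49 | 64% | 4.03 |
| Two-sided 0.05/3 | 6.41 | 35% | 3.08 |

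Every SD in the second column is above the ceiling. Power falls as the SD rises, so the third column is the lowest power that 51 per group can have at that mean, and each entry exceeds 20%.

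**Step 5. The same check in terms of n.** At SD 4.98, two-sided 0.05, 20% power needs 17 per group by the t test (16 by the normal approximation), not 51.

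**Step 6. Presumed reading, power 0.80.** SD = 10.10 / (1.960 + 0.842) = 3.60 by the normal approximation and 3.57 by the t test. That is possible on the scale, so 51 is compatible with 80% power. It does not show that 3.57 was the SD used.

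**Step 7. How much the missing SD matters.** Two-sided power with 51 evaluable per group, over an assumed range of SD:

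| Assumed SD | Power |
|---|---|
| 3.0 | 92% |
| 3.57 | 80% |
| 4.0 | 71% |
| 4.5 | 60% |

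**Step 8. Drop-out allowance.** 51/60 = 0.85, so enrolling 60 per arm allows for 15% loss. This step is internally consistent, although the rate is not stated.

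**The case against.** The strongest reply is that this is a slip of label. Writing beta where power is meant is easily recognised, the corrected reading gives an attainable SD, and no patient is recruited or treated differently as a result. On that view the impossibility argument proves only that the label is wrong. That is right as far as the sample size goes: no defect in 51 or 60 per arm has been shown. But the slip falls on the only power figure in the plan, and the missing inputs prevent a reader from checking the substitute.

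A second reply is that the missing SD, sidedness and test are a reporting gap separate from the beta error. This is fair. They are raised here because the corrected sentence cannot be verified without them, and the uncertainty in power comes from the missing SD, not from the label. The open choice of analysis and the three time points neither cause nor cure the beta error. Since the 5.4 refers to the first 24 hours, a single 24-hour comparison is the natural reading of the calculation, so the 0.05/3 row is only a robustness check.

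A third reply is that an SD of 4.5 is close to the mathematical limit and would need scores heaped near 0 and 10, so 60% power is an extreme illustration. That also stands; it marks the unfavourable end of an assumed range.

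Finally, the intended 80% is inferred and not documented. It is the conventional value and fits the arithmetic, but the sponsor has to confirm it.

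**Conclusion.** The concern holds. The stated beta of 0.80 means 20% power and cannot be true of 51 per group, a 2-point difference and a 0 to 10 score. The SD needed is 8.97 two-sided (6.41 even at 0.05/3) against a ceiling of about 5, and at that ceiling two-sided power is already 52%.

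This rests on a comparison of mean worst pain scores between two equal groups, the only endpoint that the Sample size paragraph names. That power of 0.80 was meant is a well-supported inference. Whether the trial has 80% power cannot be settled from the document, because that requires an SD of about 3.57 (two-sided) that the plan does not give. The point should be corrected, but it does not invalidate the design.

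**What to change.** Once the sponsor has confirmed the intended value, correct the figure to power 0.80 (beta 0.20). In the same sentence give the SD actually used and its source in the prior studies, whether alpha is one- or two-sided, and the test, so that 51 can be reproduced.

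The back-calculated 3.57 should not be written in as though it had been the design input. If the sourced SD does not reproduce 51, the simplest course is to keep the planned enrolment and state the power which that SD gives at 51 evaluable per group.

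The cost is one corrected sentence. Correcting the beta alters neither conduct nor enrolment. The possible consequence is in reporting: if the sourced SD differs from the implied one, the restated power may be well away from 80%, and the sponsor would have to say so.

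### Anatomic and reverse arthroplasty for three indications are pooled, but neither procedure type nor indication is on the variable list, so the planned data set cannot show case mix by arm or adjust for it

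*Combined protocol and SAP*

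**What the plan says.** All references are to the Methods of the combined protocol and SAP.

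- **Inclusion criteria, operations.** Two are eligible: "Patients undergoing unilateral primary TSA or reverse TSA". I read the first as anatomic replacement.
- **Inclusion criteria, diagnoses.** Three are eligible: "Indication for surgery is osteoarthritis, rotator cuff arthropathy or massive irreparable rotator cuff tears".
- **Randomisation.** "Randomization will be a varied blocked randomization with blocks of 12, 15 and 18 using sealed envelopes". No stratification factor is named.
- **Variables collected, pre-operative.** The list is detailed and extends to education and income. The only item describing the operation is "Side of Arthroplasty".
- **Variables collected, in hospital.** "Operative time" is listed, but it does not identify which operation was done. No heading lists procedure, implant or indication.
- **Statistics.** "Baseline data will be compared", with no variables named, and then "ANCOVA or GEE to examine differences in worst pain scores over 24 hours over time between the two groups", with no covariate named. There is no subgroup or sensitivity analysis by procedure or indication.

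**The concern.** Procedure and indication define who is eligible, yet a data set built from the list could not say how many patients had each, overall or by arm. That is a descriptive gap even if the arms turn out balanced.

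It could also matter for inference. If outcomes differ between anatomic and reverse replacement, a chance difference in the mix moves the unadjusted comparison in that particular trial, and the variation due to procedure stays in the error term. The outcomes where a dependence on the operation is plausible are arm function at 24 to 72 hours (part of the second secondary objective), six-week ASES and SANE, and total cost, which includes the index surgery. Cost bears on the rationale, because the Introduction presents the intervention as a possibly cheaper alternative. Early pain may depend on the operation too. A covariate chosen only after the results are seen would be post hoc, so the time to name it is now.

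**Working it through.** **Inputs from the protocol.** 60 patients per arm (120 in total); a 2-point target difference in worst pain; 51 per group before drop-out; no stratification.

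**Inputs assumed, because the documents give none.** The share of reverse procedures (30% to 50%); the difference in mean worst pain between procedures (1 or 2 points); the SD of worst pain.

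**1. The plan's own figure.** The Sample size section gives the mean ("the mean worst pain score in the 24 hours after surgery was 5.4, based on a 0 to 10 scale") but no SD, so 51 per group cannot be reproduced independently. Solving n = 2·SD²·(1.960 + 0.842)²/2² for n = 51 (two-sided 0.05, power 0.80) gives SD ≈ 3.6. I use 3.6 and, as a smaller alternative, 2.5. The point does not depend on the sample size being right.

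**2. How large a chance imbalance is likely.** Fix the total number of reverse cases at K and allocate 60 of the 120 patients to each arm. The number X of reverse cases in one arm is hypergeometric, and the difference in share is (2X − K)/60.

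| Reverse share | K | SD of difference | P(≥ 10 points) | P(≥ 15 points) |
|---|---|---|---|---|
| 50% | 60 | 9.2 points | 0.361 | 0.100 |
| 30% | 36 | 8.4 points | 0.319 | 0.072 |

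Two cautions apply.

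- A 10-point difference is only about one standard deviation, and the first probability column depends on including its boundary. The chance of strictly more than 10 points is 0.201 at 50% reverse and 0.163 at 30%. I therefore use the 15-point column.
- Treating the arms as two independent binomials, so that the total is not fixed, gives 27% to 32% for at least 10 points and 9% to 12% for at least 15. The order of magnitude is the same. The small effect of blocking over time is ignored.

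**3. What such an imbalance does to the pain comparison.** Shift = imbalance × difference between procedures.

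- 0.15 × 1 point = 0.15 points, which is 0.15/2 = 7.5% of the 2-point target.
- 0.15 × 2 points = 0.30 points, which is 15% of the target.

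**4. What adjustment gains in precision.** With share p reverse and procedure difference g, the fraction of variance explained is R² = g²·p(1 − p)/SD². Intervals narrow by 1 − √(1 − R²). At p = 0.5:

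| g | SD | R² | Narrowing |
|---|---|---|---|
| 1 | 2.5 | 0.25/6.25 = 4.0% | 2.0% |
| 1 | 3.6 | 0.25/12.96 = 1.9% | 1.0% |
| 2 | 2.5 | 1/6.25 = 16% | 8.3% |
| 2 | 3.6 | 1/12.96 = 7.7% | 3.9% |

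**5. Function, ASES/SANE and cost.** The documents give no SD for these outcomes and no difference between procedures, so neither calculation can be done for them.

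**The case against.** The strongest reply is that little is at risk.

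- **Validity.** A reader might infer that an imbalance would bias the trial. It would not in the systematic sense. Allocation is randomised, the unadjusted comparison is unbiased over repeated allocation, and its standard error already allows for chance imbalance. This stands. What is lost is precision conditional on the mix that actually occurs.
- **Recoverability.** A reader might also infer that an imbalance could never be seen or corrected. The documents do not support that. Indication and procedure must be known to establish eligibility, and both can be recovered from the surgical record. This stands too: the gap lies in the planned data set and analysis.
- **Prognostic importance.** Nothing in the documents shows that procedure type is the main driver of any outcome. That is a clinical judgement. Some heterogeneity is already limited: one surgeon, one anaesthetist, fractures excluded. Baseline pain, ASES and SANE are collected and could serve in an ANCOVA.
- **Primary outcome.** For pain the likely shift and the likely gain are both small, as the figures show. Six-week ASES/SANE and cost are collected variables rather than stated objectives.

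These replies limit the size of the point but do not remove it. No listed item stands in for procedure or indication, and a variable outside the data set cannot appear in the baseline comparison or in a model.

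**Conclusion.** The point holds as a cheap improvement, not as a threat to the trial's validity. As written, the plan cannot report case mix by arm or adjust for it, although it defines eligibility by exactly those two factors.

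At 60 per arm, with 30% to 50% reverse procedures assumed, a chance imbalance of 15 points or more has roughly a 7% to 10% probability. For pain the consequence is small: 0.15 points if the procedures differ by an assumed 1 point. Adjustment would narrow the pain intervals by about 1% to 2% under that assumption, or about 4% to 8% if the difference were 2 points. The primary conclusion is unlikely to turn on this. For arm function, ASES/SANE and cost the consequence may be larger or smaller, but the documents do not allow it to be quantified.

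**What to change.** 1. Add procedure (anatomic or reverse) and indication to the pre-operative variables. Record both before the allocation envelope is opened, so that they are true baseline data.
2. Name both in the baseline comparison and report them by arm.
3. Pre-specify procedure type as a fixed covariate in the pain, opioid, arm-function, ASES/SANE and cost models.

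The cost is two data fields already needed for eligibility and one degree of freedom per model. If procedure proves not to be prognostic, the gain in precision will be slight. Sample size, treatment and patient burden do not change.

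Separate envelope sets for anatomic and reverse cases are optional and not part of this fix. With 120 patients and blocks of 12, 15 and 18, a stratum of 36 would hold only two or three blocks and could end on an incomplete one. A block of 15 cannot be split equally between two arms, and a second list would carry that problem over.

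### Does a block size of 15 with no stated split, together with a stray mention of three groups, undermine the two-arm randomisation?

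*Combined protocol and SAP*

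**What the plan says.** The randomisation sentence in Methods reads: "Randomization will be a varied blocked randomization with blocks of 12, 15 and 18 using sealed envelopes". It gives no allocation ratio and no split for any of the three block sizes.

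The number of arms is given in several other places:

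- The title: "Randomized Clinical Trial of Exparel vs Pain Pump".
- The primary objective in the Introduction, which asks whether Exparel gives "better pain scores at 24, 48 and 72 hours after TSA compared to a pain pump".
- Sample size: "a sample size of 51 subjects in each group will be required", and then "a total of 60 subjects in each arm will be enrolled".
- Treatment arms, which lists one control and one interventional regimen and continues: "Both arms will receive the same multimodal analgesia medications preoperatively".

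The Statistics section has one line on worst pain, the primary outcome. It names ANCOVA or GEE and describes the comparison as "between the two groups (among the three groups". No third group is described anywhere in the document.

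**The concern.** Blocks of 12 and 18 divide evenly between two arms, but 15 does not. The person who prepares the envelopes is not told where the odd place goes. All three block sizes are also multiples of three, so they would suit a list for three equal arms or a 2:1 list. With a reference to three groups in the line for the primary outcome, a reader may wonder which design the envelopes were built for.

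Three things could be at stake: a biased or lopsided allocation, a loss of power below the planned 80%, or a primary comparison whose number of groups is unclear. A list built 2:1, or for three arms sharing 120 patients, would cost several percentage points of power or more.

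**Working it through.** **Inputs.** From Sample size: difference 2 points, alpha 0.05 (taken as two-sided), 51 evaluable and 60 enrolled per arm. The stated beta of 0.80 is read as 80% power. From the randomisation sentence: block sizes 12, 15 and 18. The SD is not stated and has to be assumed.

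**The plan's own figure.** Solving the two-sample t-test for 80% power at 51 per group gives d = 0.560, so SD = 2/0.560 = 3.57. This is the SD that the 51 implies, and the 51 cannot be reproduced independently. Enrolling 60 allows for 1 − 51/60 = 15% drop-out.

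**Divisibility.** 12/2 = 6, 15/2 = 7.5 and 18/2 = 9. Only the block of 15 is affected, and it must run 8:7 or 7:8. If all eight blocks were 15s with the same arm always favoured, the totals would be 8 × 8 = 64 and 8 × 7 = 56.

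**Worst possible list at 120.** Five blocks of 15 at 8:7 and two of 18 put 5 × 8 + 2 × 9 = 58 of the first 5 × 15 + 2 × 18 = 111 patients in one arm. If the next nine places, taken from a block of 18, all fall in that arm, it reaches 58 + 9 = 67, against 53.

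**How often imbalance occurs.** Exact enumeration, with each block size equally likely and the last block cut at 120. The 95% range is for the number in one arm; in the middle row that is the favoured arm.

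| Rule | P(60/60) | Central 95% range | P(outside 58 to 62) | P(66/54 or worse) |
|---|---|---|---|---|
| 12/15/18, direction of 8:7 random | 0.360 | 58 to 62 | 0.027 | 0.0000017 |
| 12/15/18, extra place always to one arm | 0.160 | 59 to 63 | 0.122 | 0.00004 |
| 12/18 only | 0.638 | 58 to 62 | 0.004 | 0 |

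In the middle row the mean allocation is 61.3 against 58.7.

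**Power.** Two-sample t-test with noncentrality (2/SD)/√(1/n₁ + 1/n₂). At SD 3.57:

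- 60/60: 0.560/√0.03333 = 3.07, power 86.1%.
- 64/56: 0.560/√0.03348 = 3.06, power 85.9%, a loss of 0.15 points.
- 67/53: 0.560/√0.03379 = 3.05, power 85.6%, a loss of 0.47 points.

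The effect is small because power depends on 1/n₁ + 1/n₂, which rises only from 0.03333 to 0.03379, or 1.4%, in the worst list. At SD 3.0 power goes from 95.2% at 60/60 to 94.9% at 67/53. At SD 2.5 the loss is 0.07 points.

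**After 15% drop-out.** The figures above assume none. With 15% lost from each arm, 60/60 becomes 51/51, with 80.0% power. The 64/56 case becomes 54.4/47.6, with 79.8%.

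**Bias.** With places shuffled within a block, each patient's chance of either arm is 8/15 or 7/15 in a block of 15 and 1/2 otherwise, whatever the patient's characteristics. ANCOVA and GEE both handle slightly unequal groups.

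**Number of groups.** Every place that defines the design gives two arms. One parenthesis says three, and it follows directly on the word two in the same sentence.

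**The case for a change.** The strongest case for a change is that the loss is negligible only if the list really has two near-equal arms. The text states no ratio, and the envelope list is not in the documents. Block sizes that all divide by three and a mention of three groups point the same way. A list built 2:1 would give 80/40, with 81.8% power at SD 3.57 as enrolled and about 75% after 15% drop-out (68/34). Three arms sharing 120 patients would give 69.7% for a 40 against 40 comparison. The remedy would be only a line or two of text.

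What stands is that the wording is untidy and that a carry-over from a three-group template is plausible, though the documents do not prove it. The power figures do not stand as a reading of this plan. Both 80/40 and 40/40 contradict 60 per arm, and three arms of 60 would need 180 patients. Equal arm sizes also settle the 1:1 target in substance, even though the ratio is not written out.

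The gain from a change would be slight. Dropping 15 raises the chance of exact balance from 36% to 64%, but the central 95% range stays at 58 to 62 when the direction of the 8:7 split is random. Fixing the extra place in one arm shifts that range by only one patient. Removing the parenthesis would not settle the primary analysis either: three time points and a choice between ANCOVA and GEE would remain open, and those are separate matters.

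**Conclusion.** The concern does not call for a change. The odd block is a gap in detail that a list builder fills sensibly with 8:7 splits, and a list made that way is valid as it stands. The mention of three groups is a clerical leftover that the rest of the document overrides. Run as two near-equal arms, the rule adds no bias and costs at most 0.47 percentage points of power, in a 67/53 list that is extremely unlikely; 0.15 points at 64/56 is already a strong case.

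These sizes rest on an SD of 3.57 implied by the plan's own sample size, a two-sided test and no drop-out. At smaller assumed SDs the loss is smaller still. The conclusion also takes the stated 60 per arm at face value, and nothing in the documents shows a list built otherwise.

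### Does listing the 24, 48 and 72 h outcomes under an in-hospital heading leave discharged patients unmeasured?

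*Combined protocol and SAP*

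**What the plan says.** The Introduction gives the primary objective as to "determine if Exparel leads to better pain scores at 24, 48 and 72 hours after TSA compared to a pain pump". Under Variables collected, the In Hospital block lists "Worst pain in past 24 hours at 24, 48 and 72 hours post-op". The same block holds cumulative opioid use and arm function at those three times, and two device checks: "Pump failure (Yes/No) queried at 24, 48 and 72 hours" and "Catheter migration (Yes/No) queried at 24, 48 and 72 hours". It also lists "Length of hospital stay" and, without definition, "Local anesthesia end time". The next two blocks are six weeks and three months.

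Under Treatment arms, the control arm has "a pain pump attached in the PACU infusing at 4cc/hr", and then: "The patient will go home with that device until it runs out". The documents give no discharge time, minimum stay, reservoir volume, or method of contact after discharge.

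**The concern.** The only location label on the primary outcome is one that patients leave. The plan expects control patients to be at home while the pump is still infusing, and length of stay is an observed quantity rather than a fixed one. If staff stopped collecting at discharge, the 48 and 72 h scores would exist only for those still admitted. If discharge depended on pain, those patients would be a selected group, and the selection could differ by arm. The Introduction presents outcomes beyond 24 h as the gap this trial fills, so the data at risk would be the ones that matter most.

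A second worry concerns the pump. The device checks record failure and migration, but not ordinary emptying. The data might then not show whether a 72 h score was taken against a running pump or an empty one.

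**Working it through.** **1. The plan's own figure.** The Sample size section gives a 2-point difference, alpha 0.05, 80% power (printed as beta) and 51 per group, but no SD. From n = 2(1.96 + 0.84)² SD² / 2², n = 51 implies SD = 2 × √(51/2) / 2.80 ≈ 3.60. The t-test version gives 3.57. Enrolling 60 per arm allows for 1 − 51/60 = 15% loss.

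**2. What the literal reading would cost.** Suppose measurement stops at discharge and a share of each arm leaves before 72 h. The shares are assumptions, because the documents give no length of stay. Power of a two-sided t-test for 2 points at one time point:

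| Share lost | n per arm | SD 3.57 | SD 3.0 (assumed) |
|---|---|---|---|
| 0% | 60 | 0.86 | 0.95 |
| 15% (planned allowance) | 51 | 0.80 | 0.92 |
| 25% | 45 | 0.75 | 0.88 |
| 50% | 30 | 0.57 | 0.72 |
| 75% | 15 | 0.32 | 0.42 |

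**3. Selection bias on the same reading.** Assume that there is no true 72 h effect, that only patients above one common 24 h pain threshold (the overall midpoint) stay, and that SD is 3. Then bias = ρ × SD × [λ(a) − λ(−a)], where a = (24 h effect / 2) / SD and λ is the inverse Mills ratio.

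- 24 h effect 1: a = 0.167, λ(a) − λ(−a) = 0.907 − 0.695 = 0.212. Bias is 0.5 × 3 × 0.212 = 0.32 at ρ = 0.5, and 0.13 at ρ = 0.2.
- 24 h effect 2: a = 0.333, λ(a) − λ(−a) = 1.021 − 0.598 = 0.423. Bias is 0.63 at ρ = 0.5, and 0.25 at ρ = 0.2.

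If Exparel lowers 24 h pain, the bias runs against Exparel. The correlation, the threshold rule and the SD are all assumptions.

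**4. Does the text support that reading?** Four points, taken together, say it does not.

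- The objective is set at 24, 48 and 72 h after surgery, for the trial as a whole.
- The outcome is timed from surgery, and no wording makes it conditional on still being admitted.
- The pump checks are questions put at 24, 48 and 72 h, in an arm that goes home with the device. That fits asking patients wherever they are.
- The heading sits between the pre-operative and six-week blocks, so it reads naturally as a label for the perioperative period.

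Steps 2 and 3 are therefore conditional on something the plan does not say.

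**5. Pump run-out.** At 4 cc/hr, 24, 48 and 72 h of infusion use 96, 192 and 288 cc. Without a reservoir volume, these figures cannot show whether the pump is still running at any of those times. However, letting the pump run until empty is part of the control treatment as defined. The 72 h contrast between one injection and a pump used in that way is a comparison of two strategies as delivered, and it is interpretable whether or not the reservoir is empty by then.

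**The case for a change.** The strongest case for acting is that writing down the intention is cheap: one sentence naming a call or diary, and one data field for run-out. Staff following the form literally could stop at discharge, and both secondary objectives rely on items in the same block. Enrolling more patients would not remove a selection bias.

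Part of this stands. The documents do not say how the 48 and 72 h answers are obtained from someone at home, and no item is clearly the end of the infusion. The undefined anaesthesia end time sits beside the start time and operative time, so it probably refers to the procedure.

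The step from an unstated method to an absent measurement does not stand. Early discharge is itself an inference: the go-home sentence covers the control arm only and gives no hour. The power figures also describe a complete-case test at one time point, whereas the Statistics section plans ANCOVA or GEE over time. A GEE would keep the 24 h scores of patients missing later ones, although it would not by itself cure pain-dependent loss. Finally, the fall from 0.86 starts from no loss at all. Against the planned 15% allowance, the 25% case is a fall from 0.80 to 0.75.

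**Conclusion.** This is missing operational detail and does not call for a change to the plan. The measurements are planned for every patient at fixed times after surgery. Only the means of reaching those already discharged is unstated, and a team that sends patients home with a device and means to ask about it at 72 h would fill that gap in the ordinary way. The sizes above (power of 0.75 to 0.32 at SD 3.57 for losses of 25% to 75%, and bias of about 0.1 to 0.6 points) apply only if collection ends at discharge, and they also rest on loss shares, correlations and a discharge rule that the documents do not supply. A run-out time would help describe the 48 and 72 h results, but the primary comparison does not depend on it. The conclusion rests on reading the heading as a label for the period. Explicit wording limiting collection to inpatients would reverse it, and the documents contain none.
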